6.0 ANALYSIS POPULATIONS

6.1 Modified Intent-to-Treat Population

The Intent-to-Treat (ITT) population will include all randomized patients. All efficacy analyses will be conducted on the modified ITT (mITT) population, which is defined as all randomized patients who complete the surgical procedure. In analyses based on the mITT population, subjects will be analyzed according to their randomized treatment assignment. Analyses based on the mITT population will be considered the primary analyses of efficacy.

6.2 Per Protocol Population

The Per Protocol (PP) population will include all randomized patients who have no major protocol violations. Major protocol violations will be identified based on blinded data after the study is completed, but before database lock and the unblinding of the treatment group assignments. All efficacy analyses will be repeated on this population. In analyses based on the PP population, subjects will be analyzed according to their randomized treatment assignment. Analyses based on the PP population will be considered secondary analyses of efficacy.

6.3 Safety Population

The Safety population will include all study patients who undergo surgery (implant or sham). All safety analyses and all analyses of immunogenicity variables will utilize this population. In analyses based on the Safety population, subjects will be analyzed according to the actual treatment received.

7.0 EFFICACY ANALYSES

The primary analyses of the primary efficacy endpoint will be comparisons of the least-squares mean (LSM) change from baseline in the Fugl-Meyer Motor Scale score at Week 24 of SB623 treated subjects (pooling all SB623 doses) to sham surgery control subjects for the antibody subgroup variables defined in Section 5.6. For each antibody subgroup variable, the relationship between the subgroup variable and the primary efficacy endpoint will be examined in the following manner. An analysis of covariance (ANCOVA) will be performed with terms for treatment (pooled SB623 or sham surgery), subgroup, the treatment-by-subgroup interaction, and the baseline Fugl-Meyer Motor Scale score. Within each subgroup category, the LSM and its standard error will be presented for the two treatments, together with a 95% confidence interval for the LSM. The difference in LSMs between treatments and the corresponding 95% confidence interval will also be presented, as well as the p-value for the test of the null hypothesis that the LSMs are equal for the two treatments. In order to examine whether the treatment effect differs for different categories of the subgroup variable, an F-test will be used to test the null hypothesis that the coefficient of the interaction term equals 0. Missing observations will not be imputed.

In addition, the primary efficacy endpoint, the change from baseline in the FMMS score at Week 24 among all patients, will be analyzed to examine dose response for the antibody subgroup variables defined in Section 5.6. As for the primary analysis, an analysis of covariance will be performed. The model will include terms for SB623 dose, subgroup, the SB623 dose-by-subgroup interaction, and the baseline Fugl-Meyer Motor Scale score. Dose will be treated as a continuous variable, and the control treatment will not be included in this analysis. The p-value for the test of the null hypothesis that the coefficient of SB623 dose equals 0 will be presented. In order to examine whether the dose effect differs for different values of the subgroup variable, an F-test will be used to test the null hypothesis that the coefficient of the interaction term equals 0 and the p-value will be presented.

Descriptive statistics for the FMMS score at Week 24 and the corresponding change from baseline will be presented by treatment group (control, pooled SB623, and each SB623 dose) and subgroup category for each antibody subgroup variable. Tables and graphs will be presented summarizing the mean change from baseline in the FMMS score over time by treatment group (pooled SB623 and control) and subgroup category for each antibody subgroup variable, and tables will be presented by SB623 dose group and subgroup category for each antibody subgroup variable. The tables will present descriptive statistics. The graphs will plot the mean changes (\pm standard error) over time. The graphs will also present the p-value at each post-baseline timepoint from a two-sample t-test testing the null hypothesis that the true mean change is equal for pooled SB623 and control.

8.0 IMMUNOGENICTY ANALYSES

For each treatment group (control patients, pooled SB623 patients, and each SB623 dose group) and each visit the following results will be presented:

- Number and percentage of patients positive for flow PRA class I
- Descriptive statistics for percentage PRA class I
- Number and percentage of patients positive for flow PRA class II reaction
- Descriptive statistics for percentage PRA class II
- Descriptive statistics for MFI value
- Number and percentage of patients with MFI > 1000
- Number and percentage of patients with virtual T cell positive
- Number and percentage of patients with virtual B cell positive
- Number and percentage of patients with change in donor-specific antibodies in each of the following categories: no increase; increase, not significant; increase, significant. (post-baseline visits only).

Shift tables will be presented showing the number and percentage of patients in each cross-classification category (baseline versus worst post-baseline visit, where positive and yes are worse than negative and no, respectively) for the following variables:

1. Flow PRA class I (positive or negative)
2. Flow PRA class II (positive or negative)
3. MFI > 1000 (yes or no)
4. Virtual T cell interpretation (positive or negative)
5. Virtual B cell interpretation (positive or negative)

The shift tables will be done for each treatment group (control, pooled SB623, and each SB623 dose). For variables 1, 2, 4, and 5, among patients who are negative at baseline, a two-sided Fisher's Exact Test will be used to test for a difference in the proportion of patients who are positive at any post-baseline visit between pooled SB623 and control and among the SB623 dose groups. For variable 3, among patients for whom $MFI \leq 1000$ at baseline, a two-sided Fisher's Exact Test will be used to test for a difference in the proportion of patients for whom $MFI > 1000$ at any post-baseline visit between pooled SB623 and control and among the SB623 dose groups.

The number and percentage of patients with an increase in donor-specific antibodies, either significant or not significant, at any post-baseline visit will be presented by treatment group (control patients, pooled SB623 patients, and each SB623 dose group). A two-sided Fisher's Exact Test will be used to test for a difference in proportions for pooled SB623 versus control and among SB623 dose groups. Similar analyses will be done for the number and percentage of patients with an increase in donor-specific antibodies, significant, at any post-baseline visit.

The Pearson product moment correlation between MFI and SB623 dose will be presented by visit for the following groups: all SB623 patients, SB623 patients with no pre-existing donor-specific antibodies, and SB623 patients with pre-existing donor-specific antibodies. For each group of patients, the p-value for a two-sided test based on the t-distribution of the null hypothesis of no correlation will be presented.

Figures will be presented showing the mean donor antibody specific MFI value at each visit among control patients and among the pooled SB623 patients, and also among each SB623 dose group. This will also be done for patients with pre-existing donor-specific antibodies and patients with no pre-existing donor-specific antibodies.

The relationship between whether or not the patient had a significant increase in donor-specific antibodies at any post baseline visit will be analyzed using the Cochran-Mantel-Haenszel Test with stratification by treatment (pooled SB623 and control), testing for a difference in mean degree of HLA mismatch between the significant increase in donor-specific antibodies at any post-baseline visit subgroups. For the analysis a low degree of HLA mismatch will be assigned a value of 1.5, a moderate degree of HLA mismatch will be assigned a value of 5.5, and a high degree of HLA mismatch will be assigned a value of 9. These values are the midpoints of the number of HLA mismatches for the HLA subgroups.

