3.2 Method of Assigning Subjects to Treatment

Two groups, Group 1 and Group 2, will receive SB623 and sham surgery, respectively, in a 3:1 randomization scheme. Group 1 will be further randomized in a 1:1:1 ratio to receive either 2.5 million, 5 million, or 10 million SB623 cells. Randomization will be performed via an interactive web/voice response system (IXRS). For subjects enrolled outside of Japan, the randomization will be stratified by Glasgow Outcome Scale-Extended (GOS-E) score (i.e., scores 3, 4, 5 or 6); for subjects in Japan, the randomization will not be stratified.

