5.0 STATISTICAL CONSIDERATIONS

5.1 General Methodology

The statistical analysis of the data will be performed using SAS[®] version 9.4 or higher. All statistical tests will be performed at the 0.05 significance level.

The antibody variables will be documented using summary tables and subject data listings. Continuous variables will be summarized using descriptive statistics, specifically the number of observations, mean, median, standard deviation, minimum and maximum. Categorical variables will be summarized by frequencies and percentages. For the most part results will be presented for the four treatment groups separately and the three SB623 dose groups pooled. The three SB623 dose groups will be pooled for all statistical tests comparing SB623 to sham surgery, except where noted otherwise (e.g., dose response analyses).

Data listings will be sorted by treatment group and subject ID. All date fields will be presented in a format of ddmmmyyyy (i.e., 01Jan2018) in the listings.

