9.0 SAFETY ANALYSES

The summary of AEs will be limited to treatment emergent SAEs, which are defined as any serious adverse event with onset on or after the initiation of treatment or any serious adverse event already present that worsens in intensity following exposure to study treatment.

For each treatment group (control patients, pooled SB623 patients, and each SB623 dose group) and each category of each antibody subgroup variable, the following results will be presented: number and percentage of subjects with at least one SAE and descriptive statistics for the number of SAEs per patient. For each category of each antibody subgroup variable, a two-sided Fisher's Exact Test will be used to test for a difference between treatments (pooled SB623 versus control) in the proportion of patients with at least one SAE. For each treatment group, a two-sided Fisher's Exact Test will also be used to test for a difference between categories of the subgroup variables in the proportion of patients with at least one SAE.

For each antibody subgroup variable, a logistic regression analysis of SAE incidence will be performed. The model will include terms for the antibody subgroup variable, treatment (pooled SB623 or control), and the antibody subgroup variable by treatment interaction. The p-value for each term in the model will be presented. A statistically significant interaction term would indicate that the effect of treatment on SAE occurrence is different between the two categories of the antibody subgroup variable.

For each antibody subgroup variable, a dose response analysis of the incidence of SAEs will be performed using a logistic regression model with terms for the antibody subgroup variable, SB623 dose (as a continuous variable), and the antibody subgroup variable by SB623 dose interaction. The control group will be excluded from these analyses. The p-value for each term in the model will be presented. A statistically significant interaction term would indicate that the effect of dose on SAE occurrence is different between the two categories of the antibody subgroup variable.

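### The yes/no antibody variables are compared across the three SB623 doses only with an unordered Fisher test, although the SAP models other binary outcomes with dose as continuous; an ordered test should be added beside it

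*SAP*

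**What the plan says.** SAP Appendix D (antibody plan), section 8.0, sets out two groups of yes/no comparisons, each with a two-sided Fisher's exact test.

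- **Conversion from baseline** (flow PRA class I, flow PRA class II, virtual T cell, virtual B cell, MFI above 1000), among patients negative or at or below the cut-off at baseline. The proportion positive is compared "at any post-baseline visit between pooled SB623 and control and among the SB623 dose groups".
- **Increase in donor-specific antibodies** (any increase, and significant increase, at any post-baseline visit), again "to test for a difference in proportions for pooled SB623 versus control and among SB623 dose groups".

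The doses come from Appendix D section 3.2: "Group 1 will be further randomized in a 1:1:1 ratio to receive either 2.5 million, 5 million, or 10 million SB623 cells". The level is set in section 5.1: "All statistical tests will be performed at the 0.05 significance level".

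Section 8.0 contains one ordered analysis: "The Pearson product moment correlation between MFI and SB623 dose will be presented by visit", with p-values, in three patient groups. It covers the continuous MFI value only.

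Elsewhere dose enters as a number. For efficacy in the same appendix (section 7.0): "Dose will be treated as a continuous variable, and the control treatment will not be included in this analysis". For SAEs, a binary outcome, section 9.0 fits a logistic model with terms for the antibody subgroup, "SB623 dose (as a continuous variable), and the antibody subgroup variable by SB623 dose interaction". Logistic models with continuous dose and no control arm are also planned for hematomas (Appendix E, section 8.0) and the Global Rating of Perceived Change (Appendix A, section 10.2).

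**The concern.** The natural dose question for an allogeneic cell product is whether more cells immunise more patients. A Fisher test on a 3x2 table does not ask that. It asks whether the three proportions differ in any way, and its p-value is the same if the labels 2.5, 5 and 10 million are shuffled. The SAP gives no reason for treating these seven binary variables differently from its other binary outcomes.

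Changes in serum antibodies are a listed safety endpoint (protocol section 5.2.2), and describing immunogenicity is a stated objective of Appendix D (section 2.0). The groups are small, and the conversion tests drop patients already positive at baseline. A real dose-related rise could then be missed by a test that does not use the dose order.

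**Working it through.** **Inputs from the documents.** Doses 2.5, 5 and 10 million, allocated 1:1:1; two-sided tests at 0.05 (Appendix D, sections 3.2, 5.1 and 8.0).

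**Patients per dose** (Appendix A, section 3.4). The stated sample size reproduces. The standard error is 7.25 × √(1/36 + 1/12) = 7.25 × 1/3 = 2.417, so the non-centrality is 7.0/2.417 = 2.90, and the two-sided t-test has 80.9% power with 36 and 12 patients. Then 48 × 1.08 = 51.8, or 52. SB623 patients: 52 × 3/4 = 39, and 39/3 = 13 per dose (36/3 = 12 if only the evaluable number is counted). The conversion tests have fewer; 10 per dose is taken as an assumed case.

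**Assumed.** Antibody rates: the documents give none, and they state no power for any of these tests.

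**Method.** Let a, b and c be the positives at the three doses, n per dose, m = a + b + c.

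- Probability of a table given its margins: C(n,a)·C(n,b)·C(n,c) / C(3n,m). Fisher's p-value sums this over all tables that are no more probable than the one observed. Swapping a, b and c changes nothing.
- Exact trend test: T = 2.5a + 5b + 10c, with mean m × 17.5/3 = 5.83m. The p-value sums the same probabilities over tables with |T − 5.83m| at least as large as observed.
- Power: the binomial probability of every table with p ≤ 0.05, summed over all 14³ = 2,744 tables at 13 per dose or 11³ = 1,331 at 10 per dose.

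**Rates rising roughly in line with dose** (power in %; differences taken before rounding)

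| Assumed rates | n per dose | Fisher | Exact trend | Difference |
|---|---|---|---|---|
| 5/15/40% | 13 | 46.6 | 58.8 | +12.1 |
| 10/20/50% | 13 | 51.3 | 65.5 | +14.1 |
| 20/30/60% | 13 | 43.4 | 57.9 | +14.5 |
| 5/15/40% | 10 | 29.4 | 48.1 | +18.7 |
| 10/20/50% | 10 | 36.2 | 52.4 | +16.1 |
| 20/30/60% | 10 | 33.4 | 45.2 | +11.8 |

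**Other shapes, 13 per dose**

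| Assumed rates | Fisher | Exact trend | Difference |
|---|---|---|---|
| 10/40/70% | 83.2 | 89.2 | +6.0 |
| 10/40/50% | 50.3 | 50.1 | −0.2 |
| 10/45/55% | 61.6 | 58.2 | −3.4 |
| 10/50/50% (plateau) | 59.6 | 42.4 | −17.2 |
| 10/50/30% (mid-dose peak) | 47.1 | 7.0 | −40.1 |

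**Score choice.** With equally spaced scores in place of 2.5/5/10, the first three gains at 13 per dose fall to 6.1, 5.0 and 4.0 points.

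**Type I error.** Each test alone rejects at most 4.3% of the time under equal rates at 13 or 10 per dose. The chance that at least one of the two rejects is about 5 to 6% for common rates of 20 to 50%.

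**The case against.** The strongest case for the plan as written is that nobody knows the shape of the antibody dose response, so an omnibus test is defensible. Much of this stands. The first three patterns have a second step 2.5 to 3 times the first, close to the 2:1 ratio of the dose steps, which is the shape that favours scores of 2.5/5/10. Where the response flattens above the lowest dose, Fisher is the better test, and that can happen without any fall at the top dose. The gain also shrinks under other scores, although 2.5/5/10 is the scale the SAP's own continuous-dose models imply.

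Three stronger readings are tempting, and the documents do not support them.

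- *That immunogenicity as a whole ignores dose order.* It does not: MFI is correlated with dose by visit. One of the seven variables, MFI above 1000, is a cut of that same measurement.
- *That a non-significant Fisher test will be taken as evidence of safety.* Nothing says so. Counts and percentages by dose and visit, and shift tables by dose, are all reported, and these are supportive tests without multiplicity control (Appendix D, section 5.5).
- *That a trend test would cure low power.* Protocol section 4.2 reports no antibody responses in the earlier study at the same doses. If rates are low, for example 5/10/20% at 13 per dose, power is about 9% with Fisher and 16% with the trend test. Sample size is then the limit.

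**Conclusion.** The inconsistency is real and narrow. For seven yes/no antibody variables the only among-dose test is unordered, while the SAP uses continuous dose for its other binary dose-response analyses, including SAEs in the next section of the same appendix.

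The cost is conditional. It is about 12 to 15 points of power at 13 per dose and 12 to 19 at 10 per dose, if rates rise roughly in line with dose and the scores are the doses themselves. It is small or nil for 10/40/70% and 10/40/50%, and it becomes an advantage for Fisher under a plateau or a mid-dose peak. A reader might infer that Fisher is the wrong test and should be replaced; the reversal rules that out. What is missing is an ordered test alongside it. The primary analysis is unaffected, and this is a low-priority, cheap improvement.

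**What to change.** In Appendix D section 8.0, keep every Fisher test, including pooled SB623 versus control. For each of the seven yes/no variables add, among the SB623 doses only, an exact Cochran-Armitage trend test with scores 2.5, 5 and 10. A logistic regression with continuous dose and control excluded, as planned for hematomas in Appendix E section 8.0, would also serve. State the scores in the text and report each dose's rate with an exact confidence interval, so that the reader sees the pattern and its imprecision as well as two p-values.

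The addendum to the main SAP (section 3.0) records that some analyses were added after the interim results were unblinded. If the trend test is added after that point, label it post hoc.

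The cost is a short wording change and one more option in the frequency procedure, with no new data. The downside is one extra unadjusted p-value per variable, which takes the chance of at least one false rejection per variable to about 5 to 6%.

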5.6.1 HLA Genotype

HLA typing compares donor to recipient at each of two alleles for each of the following loci:

- a. HLA-A (0 mismatch, 1 mismatch, or 2 mismatches)
- b. HLA-B (0 mismatch, 1 mismatch, or 2 mismatches)
- c. HLA-C (0 mismatch, 1 mismatch, or 2 mismatches)
- d. HLA-DRB1 (0 mismatch, 1 mismatch, or 2 mismatches)
- e. HLA-DQB1 (0 mismatch, 1 mismatch, or 2 mismatches)

These results generate the following 3 HLA subgroup categories (by adding up the number of mismatches at each locus), which will be used for the subgroup analyses:

- High degree of mismatch (8-10 mismatches)
- Moderate degree of mismatch (4-7 mismatches)
- Low degree of mismatch (0-3 mismatches)

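### The test of HLA mismatch against antibody rise scores three group midpoints although each patient's 0–10 mismatch count is known; the test stays valid but loses precision

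*SAP*

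**What the plan says.** SAP Appendix C (Genotyping), section 5.6.1, explains how mismatch is measured: "HLA typing compares donor to recipient at each of two alleles for each of the following loci". Five loci follow (HLA-A, -B, -C, -DRB1 and -DQB1), each contributing 0, 1 or 2. The subgroups are then formed "by adding up the number of mismatches at each locus": low is 0–3, moderate is 4–7 and high is 8–10.

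SAP Appendix D (Antibody), section 8.0, uses these groups in a Cochran-Mantel-Haenszel test with treatment (all SB623 doses together, or sham) as the stratum. Its aim is given as "testing for a difference in mean degree of HLA mismatch between the significant increase in donor-specific antibodies at any post-baseline visit subgroups". The scores are fixed in advance at 1.5 for low, 5.5 for moderate and 9 for high. The plan's only reason for them is: "These values are the midpoints of the number of HLA mismatches for the HLA subgroups".

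The output is Table 5.2 in Appendix D's own table list. Neither appendix gives a distribution of mismatch counts, a power target for this test, or a reason for scoring groups rather than the count.

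**The concern.** Midpoint scores are useful when only an interval is known for each patient. Here the exact value exists before grouping, because the groups are made from it. Replacing it with a midpoint stretches some one-mismatch differences and erases other, larger ones.

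As far as can be found, this is the only planned test that links mismatch to an antibody response. The Genotyping SAP relates mismatch to the Fugl-Meyer endpoint and to serious adverse events, not to antibodies. With about 52 subjects and 3:1 allocation, about 39 receive cells (52 × 3/4) and about 13 do not. An avoidable loss of precision is therefore unwelcome, even in an exploratory analysis. At stake is the chance of seeing a relation between mismatch and immunisation if there is one. Nothing about the primary endpoint is affected.

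**Working it through.** **1. Reproduce the plan's scores.** From the ranges in Appendix C, section 5.6.1: (0 + 3)/2 = 1.5; (4 + 7)/2 = 5.5; (8 + 10)/2 = 9. All three agree with Appendix D, section 8.0.

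**2. What the scores do to differences between patients.**

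| Comparison | Difference in count | Difference in score |
|---|---|---|
| 3 vs 4 | 1 | 5.5 − 1.5 = 4 |
| 7 vs 8 | 1 | 9 − 5.5 = 3.5 |
| 0 vs 3 | 3 | 0 |
| 4 vs 7 | 3 | 0 |
| 8 vs 10 | 2 | 0 |

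**3. Information kept.** If the relation with antibody rise is linear in the count, the large-sample relative efficiency of the midpoint score is r², the squared correlation between count and score. The loss is 1 − r². It depends on how counts are distributed, which the documents do not say, so several distributions are assumed.

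*Counts spread evenly over 0–10.* Mean count = 5 and variance = 10. Mean score = (4 × 1.5 + 4 × 5.5 + 3 × 9)/11 = 55/11 = 5. Score variance = (4 × 3.5² + 4 × 0.5² + 3 × 4²)/11 = 98/11 = 8.91. The covariance is also 98/11. So r² = 8.91²/(10 × 8.91) = 0.891, a loss of 11%.

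*Ten independent alleles, each mismatched with probability p (binomial).*

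| p | Low / moderate / high | r² | Loss |
|---|---|---|---|
| 0.50 | 17% / 77% / 5% | 0.641 | 36% |
| 0.60 | 5% / 78% / 17% | 0.638 | 36% |
| 0.65 | 3% / 71% / 26% | 0.659 | 34% |
| 0.70 | 1% / 61% / 38% | 0.685 | 31% |
| 0.75 | 0% / 47% / 53% | 0.699 | 30% |
| 0.80 | 0% / 32% / 68% | 0.675 | 33% |
| 0.85 | 0% / 18% / 82% | 0.584 | 42% |
| 0.90 | 0% / 7% / 93% | 0.409 | 59% |

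*Dependent alleles.* With B linked to C and DRB1 linked to DQB1, and mismatch probability 0.5–0.85, the loss is 22–35%. With beta-binomial counts (mean proportion 0.5–0.85, correlation 0.1–0.3), it is 11–28%.

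**4. Effect on power.** Suppose the count itself would give 80% power at two-sided 0.05. The score then gives Φ((1.960 + 0.842) × √r² − 1.960):

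- r² = 0.89: 2.802 × 0.943 − 1.960 = 0.68, power about 75%.
- r² = 0.67: 2.802 × 0.819 − 1.960 = 0.33, power about 63%.
- r² = 0.409: 2.802 × 0.640 − 1.960 = −0.17, power about 43%.

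The 80% starting point is only a reference, since the plan sets no target for this test.

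**5. Is the analysis still planned?** The front part of the SAP (Introduction and List of Tables) gives the comprehensive numbering for the study report. The neighbouring Antibody SAP Table 5.1, the correlation between MFI and dose, appears there as Table 14.3.5.3. No table with the title of Table 5.2 appears in that list.

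**The case against.** The strongest defence is that scoring pre-specified ordered categories by their midpoints is an ordinary mean-score method. The categories match the Genotyping SAP, and the scores are fixed in advance. They therefore introduce no bias and do not inflate type I error. The raw count has assumptions of its own: equal weight for every allele and locus, and linearity. If immunisation really jumped at 4 and 8 mismatches, the grouped score would do as well or better. All of this stands as far as validity is concerned. It does not explain the choice, because the plan justifies its scores only as midpoints of the count, that is, as a stand-in for a number already in hand.

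A reader might infer three stronger things that the documents do not support:

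- *That a third of the information is lost.* That figure needs roughly independent alleles and moderate mismatch probabilities. Other assumed distributions give 11% or 59%.
- *That the loss is like testing about 34 patients instead of 52.* The base is wrong. About 13 of the 52 are sham patients who receive no donor cells. If few of them show a donor-specific rise, their stratum adds little to a treatment-stratified test.
- *That the average score is wrong by nearly one mismatch.* Under the binomial models with p = 0.5, 0.6, 0.7 and 0.8, the typical individual error is 0.8–1.0. The mean scores, however, are 5.00, 5.87, 6.80 and 7.87 against mean counts of 5, 6, 7 and 8, so the mean is off by 0–0.2.

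Nor is it an error that the plan's mean degree differs from the mean number of mismatches. Degree is the plan's term for the three categories, and the assigned values are stated openly.

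Finally, the absence of the table from the integrated list may mean that the analysis was dropped. The appendix text, kept there for reference, still specifies the test, and no reason for the omission is given.

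**Conclusion.** The point holds as a modest, free gain in precision. The plan replaces a known 0–10 count with a three-level score meant to approximate it. Information is lost under every distribution tried: about 11% if counts are evenly spread, about 30–36% for independent alleles at the values of p tried from 0.5 to 0.8, and up to about 59% at 0.9. These figures rest on an assumed distribution of counts and on a relation linear in the count; no single figure can be taken from the documents. If nearly all patients fall in one group, the grouped test has almost nothing to compare, and it cannot be computed if all do. The count can still be used whenever counts differ.

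The consequence is limited. The test remains valid, the analysis is exploratory with no multiplicity control, and the primary endpoint is untouched. Severity is low.

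**What to change.** In Appendix D, section 8.0, use the actual number of mismatches (0–10) as the score in the same treatment-stratified Cochran-Mantel-Haenszel mean-score test. Keep low, moderate and high for display, so that the tables stay consistent with the Genotyping SAP.

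Also state whether Antibody SAP Table 5.2 is still planned. If it is, add it to the integrated table list; if not, record that it was dropped and why.

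The cost is negligible. The count is already derived for every typed patient, no new data are needed, and the test and its stratification do not change. If results have already been unblinded when the change is made, report the count-based result alongside the specified one and label it post hoc.
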